After informed consent by the subject and parent/caregiver (if applicable), each subject will complete an initial assessment during which the Speech Pathologist will select the appropriate tool(s) from the Easy Stretch Toolkit and provide training to the subject and/or caregivers in use of the device(s). During each visit, the Speech Pathologists will select the desired tools from the Toolkit and their accompanying oral placement. The recommended photographs of the 9 facial expressions will be taken via screen shots. Education will be provided regarding tool selection and placement location during each weekly visit. Participants will need to return their homework sheets and self-made photographs of each facial expression via email to the Speech Pathologists each week or by mail at the end of the study period.

The tools are available in small, medium and large sizes. The small to medium sizes for each shape should be the correct size for children's mouths. Subjects and caregivers (may be parent or guardian, in the case of pediatric population) will be trained until they can demonstrate independent carryover of the placement and verbal confirmation of the prescribed protocol. See attachment for patient/caregiver education materials to be used, which will include written instructions for the patient (Appendix I). Data to be gathered includes pupil distance, VROM, HROM and facial measurements at rest and while the subject is completing specific facial movements, with goal of demonstrating increased range of motion of the oral musculature and improved facial and scar appearance over time (Appendix H). Initially it will be proposed that the chosen head shape be used [name] and [name]
Version 10/October 2020
Page 6 of 24

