for 60 minutes (+/- 10 minutes) 2 times per day for each day of the study. Frequency of use of the device will be closely documented by the Speech Pathologists and the patient or caregiver using the provided charting system (Appendix I). Because use of the devices will be prescriptive, the applicable head shape(s) and placement(s) will vary by individual and by week. Specifically, placement(s) is (are) expected to vary each week based on the clinical needs of the subject and outcomes seen from the prior week's intervention. For monitoring purposes, data will be gathered at the initial assessment and 1 time per week thereafter (+/- 2 days) for the duration of the 8 week trial. As a result, data will be evaluated as to the prescriptive plan for deficits for specific facial landmarks and their associated muscle groups (cheeks, nasolabial folds, upper lip, mentolabial junction and modiolus). Subject safety will be met via an initial training session and weekly one-on-one follow-up visits via FaceTime, Skype or in person visit with the monitoring Speech Pathologist to assure appropriate use of the devices. Patient (or parent) handouts (Appendix I) will be provided to assist with recording of time spent using the devices and with which tool and placement location.

Assessment of the patient after completion of informed consent

- Photograph of the patient's face from the front, as well as their side profile (weekly), with measurements taken from the photograph at specific points. At this time, profile photographs will not be used for measurements or analysis but will be kept to show visual changes over time.
- Oral-motor facial examination will be conducted.

Targeted muscle groups [8]

The facial muscles to be targeted include:

- Levator labii superioris – elevates the upper lip and deepens nasolabial furrow
- Buccinator – controls movement of the cheeks and assists in sucking in neonates and mastication in pediatrics and adults
- Depressor anguli oris – assists with frowning, pulls corner of mouth inferiorly
- Mentalis – protrudes lower lip, inward and upward movement of the soft tissue of the chin
- Zygomaticus major – pulls angle of mouth upward and laterally
- Zygomaticus minor – raises upper lip
- Nasalis – compresses bridge, depresses tip of nose, elevates corners of nostrils
- Levator anguli oris – assists with smiling, elevates angle of the mouth
- Depressor septi – depression of the nasal septum

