- Risorius – draws back the angle of the mouth laterally
- Depressor labii inferioris – depression of the lower lip
- Obicularis oris – sphincter around the mouth, brings lips together, retracts lower lip

Measuring Outcomes

The investigators will use photographs of the patient to measure multiple facial features and excursions during movement. Required materials include: a set of the Easy Stretch devices, departmental iPad with iPad stand or access to personal computer or smartphone, UTMB customized facial measurement software, computer, CEN-TECH 6" digital caliper.

Pictures will be taken with the patients in a seated position and head in neutral and midline position. Subjects will be asked to take photos with their eyes open and their face fully within the frame. A single blinded observer will be used to complete the measurements taken in the facial measurement system.

Measurements to be taken:

- Pupil distance
- Horizontal distance between outside of nares
- Pupil to outside of nares (right and left)
- Pupil to outside corner of lip (right and left)
- Superior edge of philtrum to outside corner of lip (right and left)
- Nares to outside corner of mouth (left and right)
- Length of philtrum
- Superior border of upper lip to inferior border of lower lip
- Horizontal distance between outside corners of lips
- Inferior border of lower lip to inferior tip of chin

Measurements will be taken during each of the following targeted facial expressions:

- At rest
- Wrinkle the nose
- Gentle smile
- Broad smile with lips closed
- Broad smile with teeth together
- Vocalizing prolonged “eee” sound
- Vocalizing prolonged “ooo” sound
- Lip pucker
- Mouth opening as measured by distance between inferior upper lip and superior lower lip

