The customized UTMB facial software is a two dimensional measurement system. Jorge Jr., et al, provided a summary of several past and present measurement systems, considered as subjective vs objective and simple vs complex, in their article exploring measurement of peripheral facial paralysis [9]. Although a three dimensional measurement system such as the Vicon system [9] is beneficial for quantifying measurements across multiple axes especially the anteroposterior axis, the creators chose to pursue a two dimensional measurement system for its cost effectiveness and ease of use. The UTMB customized facial software is based upon use of pupil distance, as this is a static landmark and subsequent measurements can be graded based on this measurement. Fields and Peckitt performed a similar measurement in their study, called the Facial Nerve Functional Index, measuring percentage change from the corner of the lip with a mouth closed position to the external corner of the ipsilateral eye vs smiling broadly [9]. In their 2015 article on use of their 3D dynamic quantitative analysis system of facial motion (3D ASFM) and assessment of mimic muscles during facial contraction, Feng et al proposed that the mouth-eye association and their related movements have the greatest influence on quality of life [10].

Endpoints include degree of excursion during different facial movements. Description of change will be documented in degree of difference in millimeters of movement when producing each expression with subsequent statistical analysis to determine that mean changes and variation of changes, and if

change was not the result of chance. Multiple studies have attempted to define a “normal” range of motion [9,11]. Specifically, although facial landmarks are consistent, it must be considered that there are differences in facial expressions and excursions within the same individual for both sides of the face, as well as between individuals of different races, ages and gender [9]. For this reason, the creators are unable to predict a percent change as there are currently no consistent norms for range of motion and excursions of facial landmarks. Therefore, change will be evaluated within a single subject over completion of the course of treatment.

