The investigators would like to request a waiver of written consent to verbally screen potential subjects via phone, electronic media or in person using the eligibility checklist and inclusion/exclusion criteria, prior to their first visit when they will sign the consent document. Because the investigators are pursuing multiple recruitment avenues apart from chart review, a flexible screening process is necessary.

At the time of the initial contact with the patient, a full description of the study will be provided. Consent will be obtained prior to or at the beginning of the first treatment session. In the case of a pediatric subject, verbal assent will be obtained for children ages 7-12 and written assent will be obtained for children ages 13-17. Parental permission will be obtained via the consent form as parent/guardian is now included as part of that consent form.

At the time of consent a detailed medical history form and written consent for participation will be obtained by the investigators. A copy of the consent form will be mailed to the subject. Ongoing participation in the study will be reviewed during the weekly visits. Subjects will be scheduled for an immediate start date.

10. Potential Risks:

Adverse effects are not expected. However, potential risks include possibilities for: discomfort from stretching, bleeding if facial burn sites are not fully healed, allergy from intraoral contact with food-grade silicone, asymmetrical range of motion, and possible tears through the burned skin. The handle is designed to reduce the risk of choking as the subject or caregiver should be holding onto the device when using it. However, there is a remote choking risk if the subject uses the device incorrectly (such as chewing on the device, sucking on the device or removing the head of the device from the handle).

11. Subject Safety and Data Monitoring:

The PI will review the safety of these interventions with [name], Faculty Sponsor, at 6 month intervals. Significant problems related to insertion of the device such as bleeding, choking will be reported to the IRB immediately. Any related or unrelated adverse events will be reported in a timely manner to the IRB.

12. Procedures to Maintain Confidentiality:

Pictures will be taken using a departmental iPad and patient data will be stored on secure UTMB computers. Patient's written or verbal consent will be obtained prior to photographing the patient.

13. Potential Benefits:

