Expected benefits include: increasing range of motion for multiple facial muscles and tissues; reducing the impact and appearance of scar tissue; ability to target multiple sites across the face, with particular attention to the cheeks, nasolabial folds, upper lip, mentolabial junction and modiolus; achieving a stretch that currently available tools cannot provide; improved ability to produce different facial expressions; increased speech intelligibility; improved ability to complete oral hygiene.

14. Biostatistics:

Sample size calculation shows that a sample size of 20 (accounting for 10% missing rate) will be able to detect an effect size of 0.7 by using a two-sided paired t-test, if the real study has statistical power of 0.8 and the significance level (alpha) is 0.050.

Descriptive statistics for continuous and categorical variables will be presented as mean \pm SD and quartiles, and frequencies and proportions, respectively. For the weekly measurements, we will use the descriptive statistics and individual trend plots to present the data. The primary outcome is the change in millimeters after the completion of treatment (post – pre measures) for each facial expression. We will use paired t-tests (if data is normally distributed) or non-parametric alternatives (e.g., Wilcoxon signed-rank test) to test if the changes are statistically significant. The change score of facial disability index (FDI) will be analyzed using the same method. The pre-post outcome of the cranial nerve assessment will be classified by categories (Pass-

Pass, Fail-Pass, Fail-Fail), and the frequencies and proportions will be reported. Two-sided statistical significance will be considered for alpha at the 0.05 level for all tests.

References:

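### The plan does not say which photograph is measured or hold camera distance constant, so the pupil-scaled millimetre outcome can shift between visits when the face has not changed

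*Combined protocol and SAP*

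**What the plan says.** Several routes to a photograph are open at once.

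- Section 4, Measuring Outcomes, lists as equipment a "departmental iPad with iPad stand or access to personal computer or smartphone".
- Section 4, Protocol, says that "photographs of the 9 facial expressions will be taken via screen shots". It also asks participants to return "self-made photographs of each facial expression via email" each week, or by mail at the end.
- The same section provides for weekly "follow-up visits via FaceTime, Skype or in person visit".
- Section 12 says: "Pictures will be taken using a departmental iPad and patient data will be stored on secure UTMB computers".

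On measurement, Section 4 states: "The customized UTMB facial software is a two dimensional measurement system". It scales on pupil distance as a fixed landmark. The text grants that a three-dimensional system is better along the front-to-back axis, and chooses two dimensions for cost and ease of use.

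The stated controls on the picture are a seated position, a neutral midline head, open eyes, a face wholly inside the frame, and one blinded observer. Appendix H has tick boxes for the pictures taken but no field for source, device or distance.

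Section 14 defines the primary outcome as the post minus pre change in millimetres for each facial expression. Section 4 speaks instead of excursion and degree of movement. Neither says whether the rest photograph is subtracted.

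**The concern.** Scaling on the pupils corrects for camera distance only for points in the plane of the pupils. A length nearer the camera than that plane is magnified relative to the pupils, and more so when the camera is close. If the mouth region lies in front of the pupils, the same mouth therefore measures wider from a near camera than from a far one. None of the stated controls fixes distance: a face can fill the frame of a hand-held phone, a laptop or an iPad on a stand at quite different distances.

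The outcome is a within-person difference, and each participant is his or her own control (Section 3). Any change of distance between baseline and the final visit goes straight into that difference, and there is no comparison group in which a shared shift would show up. Section 2 plans to power a larger trial on the effect sizes found here, so the error would carry forward.

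**Working it through.** **1. The plan's own figure.** Section 14 says that 20 participants with 10% missing "will be able to detect an effect size of 0.7" with power 0.8 at two-sided alpha 0.05. For a paired t-test the exact requirement is n = 18.03. Analysed n = 20 × (1 − 0.10) = 18, where power is 0.799. The figure reproduces. It is in standardised units; the plan gives no millimetre SD and no measurement-error figure.

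**2. Geometry.** Let D be the distance from camera to pupil plane, z the distance of the mouth in front of that plane, L the true length and P the pupil distance. With focal length f, the pinhole images are fL/(D − z) and fP/D. After scaling on the pupils:

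measured length = P × [fL/(D − z)] ÷ [fP/D] = L × D/(D − z)

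The focal length cancels, so in this model distance matters and the device does not. The plan gives no D, z or L. Assumed: L = 50 mm (lip width), z = 10, 20 or 30 mm, D = 300, 400 or 600 mm.

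| z (mm) | D = 600 | D = 400 | D = 300 | 600 to 400 | 600 to 300 |
|---|---|---|---|---|---|
| 10 | 50.85 | 51.28 | 51.72 | +0.43 | +0.88 |
| 20 | 51.72 | 52.63 | 53.57 | +0.91 | +1.85 |
| 30 | 52.63 | 54.05 | 55.56 | +1.42 | +2.92 |

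With the same distance at both visits the shift is zero.

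**3. How far this generalises.** The shift is proportional to L, so a 20 mm length at z = 20 mm moves 1.85 × 20/50 = 0.74 mm for 600 to 300 mm. A smaller move (600 to 500 mm, L = 50, z = 10) gives 0.17 mm. A larger one (1000 to 300 mm, L = 60, z = 25) gives 3.92 mm. The table is an illustration and not a bound. The formula applies to lengths at a single depth; distances from pupil to lip corner span two depths and would shift by other amounts.

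**4. If rest is subtracted within the session.** Assume rest 50 mm and expression 60 mm, a true excursion of 10 mm. At constant depth the shift is 10/50 of the table: 0.09 to 0.28 mm (600 to 400) and 0.18 to 0.58 mm (600 to 300). Now let the lips retract 0, 5 or 8 mm during the expression, with rest depth 10 to 25 mm and distance pairs between 300 and 1000 mm. The shift is then 0.03 to 0.94 mm in absolute value, and its sign can reverse. The extreme case is z = 10, retraction 8, 1000 to 300 mm:

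- near: 60 × 300/298 − 50 × 300/290 = 60.40 − 51.72 = 8.68
- far: 60 × 1000/998 − 50 × 1000/990 = 60.12 − 50.51 = 9.62 (rounded after subtraction)
- shift: −0.94 mm

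Rest is itself one of the nine listed expressions. It has no excursion, so a rest measurement stays raw.

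**5. Consequence for the test.** Assume an SD of true change of 2, 3 or 5 mm and 18 analysed. Added error with SD s and no common direction lowers the standardised effect to 0.7 × SD/√(SD² + s²). A common shift with no true change raises the chance of a significant result above 0.05.

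| SD of change (mm) | power, s = 1 | power, s = 2 | P(significant), common shift 1 mm | common shift 2 mm |
|---|---|---|---|---|
| 2 | 0.71 | 0.51 | 0.52 | 0.98 |
| 3 | 0.76 | 0.64 | 0.27 | 0.76 |
| 5 | 0.78 | 0.74 | 0.13 | 0.36 |

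**The case against.** The strongest reply is that the raw lip width may be the wrong quantity. Section 4 describes the endpoint as excursion, and a rest photograph is taken at every visit. If movement is expression minus rest in one session, most of the scale error cancels and what remains is under about 1 mm. This stands as far as it goes, but Section 14's wording equally permits raw post minus pre distances, and the documents do not settle it.

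Second, the choice of two dimensions is disclosed and reasoned, in a 20-person pilot that controls posture, head position and observer. Also true; but accepting a two-dimensional system does not prevent holding distance constant within a participant.

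Third, telehealth reads as an option elected at enrolment, so switching may be rare. The text does not forbid switching, however, and a participant who stays on telehealth with a hand-held phone still has no set distance.

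Fourth, the Appendix K figure was not available for this review, and the education materials are a separate attachment. Either might contain instructions on distance. The text describing the software mentions no depth correction.

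**Conclusion.** The gap is real and modest in size. The visible plan leaves the measured image unnamed and the camera distance free between pre and post. Under the assumed inputs this moves a raw 50 mm lip width by 0.4 to 1.4 mm (60 to 40 cm) or 0.9 to 2.9 mm (60 to 30 cm), shorter lengths by less, and a within-session excursion by about 0.03 to 0.94 mm. All of these rest on assumed depth, length and distance, none of which is in the documents.

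A reader might infer more, and four stronger readings are not supported:

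- That a change of device alone shifts the outcome. In this geometry a new device at the same distance gives no shift; lens distortion was not computed.
- That the trial will be biased toward benefit. Nothing in the documents suggests that distances shorten over the study or that participants move from clinic to home. Without a common direction the effect is mainly noise. A common drift would be bias, and this design could not detect it.
- That all lower-face distances move together by a similar amount. Only single-depth lengths were computed, and the listed measurements differ in length and depth.
- That the sample size is wrong. It reproduces on its stated inputs.

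The point merits a change because the error is avoidable at little cost.

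**What to change.** In Section 4, Measuring Outcomes:

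1. Name one image as the measured image: the Speech Pathologist's screen shot or iPad photograph, with self-made pictures as backup only. Bring Section 12 into line.
2. For each participant, set the source, device and camera-to-face distance at baseline and keep them for every later photograph. A cord of set length in the mailed package would fix the distance at home.
3. State that movement is computed as expression minus rest from the same session, and use the same definition in Section 14.
4. Add fields for source, device and distance to Appendix H.

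In Section 14, add a repeat of the primary analysis that leaves out participants whose pre and post setup differs.

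The cost is a cord in the kit, a line on the weekly form, a few sentences of protocol text and one sensitivity analysis. The small downside is less freedom to switch visit mode during the eight weeks.

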Easy Stretch Toolkit: A Pilot Study

Co-Investigators: [name] and [name]

Funding Sponsor: UTMB Health Technology Commercialization Program

Version 10/October 2020

Efficacy of the Easy Stretch Toolkit: A Pilot Study

1. Introduction and Purpose:

The Easy Stretch Toolkit (patent pending) is a set of three novel intraoral tools designed to deliver a passive stretch to scarred or contracted orofacial musculature, with the goals of: 1) increasing measurable range of motion for multiple facial muscles and tissues, and 2) reducing the impact and appearance of scar tissue. We designed the Easy Stretch Toolkit for patients negatively impacted by facial burns. We propose a pilot study to test if the tools can directly target multiple sites across the face, with particular attention to the cheeks, nasolabial folds, upper lip, mentolabial junction and modiolus, achieving a stretch that currently available tools cannot provide. We hypothesize that there will be an expected gain of improved ability to increase use of orofacial musculature, as well as improved range of facial expressions and related motor functions in patients with facial burn injury. The Easy Stretch Toolkit is proposed for use with adults and children over the age of 7 in this pilot study. Use of the device(s) is intended to be utilized by a trained Speech Pathologist. The exact tool to be used will be selected by the Speech Pathologist based on the patient's specific deficit areas and needs. In this pilot study, investigation into the efficacy of the Toolkit will be limited to subjects with chronic facial burns, with future plans to expand the project to subjects of all ages in the acute healing phase if preliminary results prove the tools are effective. Physical prototypes were created with the assistance of the MakerHealth Space Lab at UTMB, following the designs and initial prototypes of the creators (patent pending). See Appendix A. The current treatment options for patients with scars secondary to orofacial burns are discussed in the Background and pictures of tools are shown in Appendix B-F. Because our tools are similar, and in some ways potentially safer than the current tools available in the market, we believe that the Easy Stretch Tools are a minimal risk device. This product represents an advance in the care of these patients. There is minimal risk associated with correct use of the product (discomfort from stretching, bleeding if facial burn sites are not fully healed, possible allergy from intraoral contact with food-grade silicone, remote choking risk, asymmetrical range of motion, remote tearing of the mucous membrane); the expected benefits are that the tools will increase mobility of the orofacial skin and musculature, as well as reduce and possibly prevent burn-induced scar formation. This protocol and enrollment procedures are revised due to the Covid -19 Pandemic to allow for increased ability to enroll participants due to the University's restrictions on travel.

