The Easy Stretch Toolkit is manufactured at UTMB in the MakerHealth Space Lab. Three dimensional images of both the handles and heads were created in the computer 3D CAD application, *Fusion 360*. Two types of tool handles were created, the L shape and the T shape with the program *Adobe Illustrator* using the dimensions from the *Fusion 360* designs. The designs for each handle were then loaded into the program for a Universal Laser Cutter, which replicated the design and engraved the handles.

Sheets of Delrin, a high-tension impervious plastic, were used to cut out the handles. Delrin was selected due its known FDA approval for use in the food industry and for its ability to withstand autoclaving. After the handle is cut using the laser cutter machine, each handle is inspected for rough edges and sanded with a fine grit sandpaper as needed.

The head shapes from *Fusion 360* were then used to create one and two piece 3D molds. These molds were then exported to a program called *Curio*, which sends the images to the *Ultimaker* 3D printer. Once printed, the molds are removed from the machine and filled. A handle is seated in the mold and Sorta Clear 40 Smooth On food grade silicone is mixed per instructions in a 10:1 ratio and poured into the molds. Sorta Clear 40 Smooth On was selected, as it is a known food grade silicone and has the ability to withstand high temperatures in autoclaving. Once filled, the molds sit for 16 hours to fully cure/set. The tools are removed from the molds and any redundant silicone is trimmed off with scissors. A small dot of medical grade silicone glue is then placed where the stick and head attach to increase security of the head on the stick. As previously noted above, the material used to assist in securing the head of the tool to the stick is a medical grade epoxy that is FDA approved for Grade IV medical devices. Once cured, the device in its entirety had stood up to high level disinfecting and autoclaving. Sterilization has been confirmed with the Resi-Test along with the Sterigage Steam indicator.

Each tool is then wiped with an enzymatic wipe and autoclaved at 260 degrees using a pass/fail indicator. Each “passed” tool will be available for use in the study. Any tool failed will be removed from the package, re-cleaned and re-autoclaved.

Tools available for the study are then labeled on the outside of the autoclave package using a Dymo Label maker stating “Investigational Tool for research purposes only”.

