1. planned or unplanned surgeries for facial skin grafting around lips or nose or oral commissure release during the upcoming 8 weeks
2. completion of any massaging or other stretching exercises or programs not specified by the creators
3. use of new creams or topical treatments for the duration of enrollment in the study.
4. acutely burn-injured patients
5. incarceration, or pregnancy

9. Sources of Research Material:

We are collecting clinical and demographic data from the electronic charts. We are also collecting data as shown in Appendix H, I, J, K, L. These will be obtained via photographs of the subject during different facial expressions which are uploaded into a software program for measurements to be taken.

9. Recruitment Methods and Consenting Process:

The investigators will request a HIPPA Waiver to identify potential subjects. Potential subjects may be patients or former patients of the investigators. Additionally, they may be identified via clinic lists or outside referral sources. The potential subjects will be identified / referred by any clinician or physician and their patient(s) will be sent a recruitment letter or informational pamphlet with the approval of the referring clinician/physician (see Appendix L, as well as recruitment brochure).

To further clarify, the investigators will pursue various methods for recruiting subjects, including UTMB or outside physician referrals, outside speech pathologist referrals, referrals from other professionals and community engagement activities. We do not plan a multisite study, but seek the option to widen the scope of patient referrals by contacting other burn centers and burn support groups and through participation in community outreach activities. The physicians will be asked to refer eligible patients; the physicians would not be engaged in the research. Subjects will be seen at their place of residence or UTMB outpatient clinics or via telehealth. Subjects may self-refer from marketing materials. Outreach will include social media, such as postings to burn support group websites or Facebook pages, Speech Pathology special interest group pages, Facebook, UTMB Department of Otolaryngology Facebook page. In all recruitment scenarios, the investigators will notify the subject's managing physician of their participation in the study. If the subject cannot be reached by phone, a letter will mailed to the potential subject with study information.

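### Silicone allergy is a named risk of the device, but no written eligibility criterion addresses it; separately, the bonding material is described in two incompatible ways

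*Combined protocol and SAP*

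**What the plan says.** **Risk.** Section 1 (Introduction and Purpose) includes "possible allergy from intraoral contact with food-grade silicone" among the risks of correct use. Section 10 (Potential Risks) repeats it: "allergy from intraoral contact with food-grade silicone".

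**Material.** Section 3 (Experimental Device) says of the heads: "Sorta Clear 40 Smooth On food grade silicone is mixed per instructions in a 10:1 ratio and poured into the molds". On the joint between head and handle it says "A small dot of medical grade silicone glue is then placed where the stick and head attach". Later in the same paragraph it says "the material used to assist in securing the head of the tool to the stick is a medical grade epoxy".

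**Eligibility.** Section 7 has five exclusions: certain facial surgery, other massage or stretching, new creams or topical treatments, acute burn injury, and "incarceration, or pregnancy". Section 6 has eight inclusion criteria. None of the thirteen mentions allergy or sensitivity.

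**Use and screening.** Section 4 initially proposes use "for 60 minutes (+/- 10 minutes) 2 times per day for each day of the study", over an 8-week treatment period. It allows eligibility to be determined by telephone, with consent given verbally and a full set of tools then sent by mail. Section 9 (Recruitment Methods and Consenting Process) refers to an eligibility checklist used together with the inclusion and exclusion criteria, and to a medical history form completed at consent.

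**The concern.** The plan foresees a specific hypersensitivity reaction to the material placed in the mouth, but its eligibility rules do not act on that knowledge. Allergy differs from most of the other listed risks because a candidate may already know of it, so one question before exposure could avoid the harm. The plan has already made this kind of link once: it lists bleeding from burn sites that have not healed, and it excludes acute burns. Allergy has no such counterpart.

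What is at stake is participant safety in the first study of this product, which enrols from age 7 and relies on home use. The analysis is not affected.

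The two descriptions of the bonding material raise a related but separate question. The risk lists name only food-grade silicone. If the joint is in fact bonded with epoxy, a question about silicone alone would not cover everything in the device.

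**Working it through.** No statistical figure of the plan is in dispute, so the check is mainly a comparison of sections.

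1. **Is the risk the plan's own?** Yes. Sections 1 and 10 name it, and Section 3 confirms that the heads are silicone.

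2. **Does any criterion address it?** No. Sections 6 and 7 are complete in the available text: 8 + 5 = 13 criteria, none on allergy.

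3. **Does another step make it disqualifying?**
   - *Medical history (Section 9) and case history (Section 4):* the information is collected, but no rule says what follows if an allergy is reported.
   - *Eligibility checklist (Section 9):* not in the available text and not listed in the appendix legend, so its content is unknown.
   - *Exit conditions (Section 3):* the examples are non-compliance, withdrawal of consent and unexpected surgery.
   - *Safety reporting (Section 11):* any adverse event goes to the IRB, but that applies after exposure.

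4. **How much exposure does the initial schedule imply?** Inputs: 60 min per session with a window of 10 min either way, 2 sessions a day (Section 4), and 8 weeks × 7 = 56 days.

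| Minutes per session | Per day | Over 56 days |
|---|---|---|
| 50 | 2 × 50 = 100 min | 56 × 100 / 60 = 93 h |
| 60 | 2 × 60 = 120 min | 56 × 120 / 60 = 112 h |
| 70 | 2 × 70 = 140 min | 56 × 140 / 60 = 131 h |

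This assumes full adherence and that the initial schedule is kept throughout. It measures contact time, not the probability of a reaction.

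5. **Are the two bonding descriptions compatible?** No. One says silicone glue and the other says epoxy. The second presents itself as restating something said earlier, but the earlier statement is the silicone glue. The text does not say whether the joint touches the mouth.

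6. **Does the sample size depend on any of this?** No. As background, a two-sided paired t-test with effect size 0.7 and alpha 0.05 has power 0.799 with 18 evaluable participants, and 18 / (1 − 0.10) = 20, the plan's figure in Section 14. The eligibility point leaves it unchanged.

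**The case against.** The strongest reply is that the text shows only an absent criterion. Candidates receive a full description of the study, are screened with a checklist, and give a history; for telehealth participants, Section 4 describes the tools as mailed after that. The speech pathologist trains each participant and sees them weekly. Any of these steps might bring an allergy to light. This stands in part: a reader might infer that the plan would enrol an allergic person, but the unseen checklist and history form prevent that conclusion. What can be said is that no written criterion bars enrolment.

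Other stronger readings are also unsupported:

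- **That the gap contradicts the minimal-risk statement.** Section 1 lists possible allergy within that very statement. A named risk with no matching exclusion is an omission. Discomfort and asymmetrical range of motion have no matching exclusion either.
- **That a reaction would cost the final measurement and use up part of the 10% missing-data allowance.** No section says that a reaction ends participation. The primary outcome is measured from photographs, which can be taken from someone no longer using the device.
- **That the glue and epoxy conflict creates the eligibility gap.** It does not. The gap would exist with a consistent description, and the conflict concerns a small amount of adhesive that both sentences call medical grade.

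It is also fair to say that the documents name neither epoxy nor the handle plastic as an allergy risk. That is why the materials to be covered should follow from a corrected device description and not from a reviewer's guess.

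**Conclusion.** The point holds in a limited form. The protocol twice names silicone allergy as a risk, yet its written criteria leave a person with a known silicone allergy eligible for about 2 h of intraoral contact a day (100 to 140 min), or about 112 h over the treatment period (93 to 131 h). The Section 3 conflict over the bonding material is a second, independent defect. It matters here because it leaves unclear which materials the screen and the risk disclosure should name.

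How often this would matter is unknown, since the documents give no allergy prevalence and none is assumed here. The conclusion rests on the criteria in Sections 6 and 7, which are fully visible. It would weaken if the checklist or history form already contains an allergy question with a stated consequence. The estimand, power and analysis are unaffected. Correction is still worthwhile because the plan itself foresees the harm and the change is small.

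**What to change.** 1. Reconcile Section 7 and the eligibility checklist with the risk lists in Sections 1 and 10 by adding an entry on known allergy or hypersensitivity to the device's contact materials. The clinical wording is for the sponsor and the investigators. If the checklist already covers this, carry it into Section 7 so that the two agree.
2. Place the question at the screening contact, before any tools are mailed, and state in Section 9 how a positive answer bears on eligibility.
3. Reconcile the two Section 3 sentences so that the bonding material named is the one actually used. Then check that the screening question and the risk lists in Sections 1 and 10 name the materials the participant will contact.

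The cost is one criterion line, one screening question and one corrected device description. Very few candidates should be lost, although without a prevalence figure this is a judgement. Sample size, schedule, endpoints and analysis stay as they are.
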